2. OBJECTIVES

2.1. Primary Objective

1. To evaluate the proportion of missed TB cases in HIV-infected children with presumptive TB not initiated on treatment as per the PAANTHER TB treatment decision algorithm (false negative cases)

2.2. Secondary objectives

- 1. To evaluate the feasibility of the PAANTHER TB treatment decision algorithm in HIVinfected children with presumptive TB
- 2. To assess the proportion of HIV-infected children with unlikely TB among those initiated on treatment as per the PAANTHER TB treatment decision algorithm
- 3. In HIV-infected children with presumptive TB, including comparison of those initiated and those not initiated on TB treatment as per the PAANTHER TB treatment decision algorithm, to assess:
 - a. Incidence of morbidity (drug toxicity, opportunistic infections, IRIS) and mortality during 6 months after enrolment
 - b. Time to ART initiation in those who are ART-naïve
 - c. Immunologic evolution at 6 months after enrolment
- 4. To assess TB treatment outcomes in HIV-infected children initiated on treatment as per the PAANTHER TB treatment decision algorithm
- 5. To assess the feasibility of IPT initiation in HIV-infected children not initiated on treatment as per the PAANTHER TB treatment decision algorithm
- 6. To assess the performance of the MLR and the C-reactive protein (CRP) and their potential added value in the PAANTHER score and algorithm to detect TB
- 7. To evaluate the diagnostic performance of Ultra performed on one NPA and one stool sample against mycobacterial culture performed on standard samples (GA in younger children or expectorated sputum in older children) in HIV-infected children
- 8. To assess the feasibility of stool sample collection, and the feasibility, safety, and tolerability of NPA collection in HIV-infected children
- 9. To assess the performance of the PAANTHER algorithm for TB diagnosis across various ages, CD4 counts, nutritional statuses, and timings of ART initiation
- 10. To evaluate the cost effectiveness of implementing the PAANTHER TB treatment decision algorithm compared to the estimated effect of the standard of care in children with HIV

3. STUDY ENDPOINTS

- 3.1. Primary study endpoint
 - 1. Proportion of missed TB cases (false negative cases) in children not initiated on treatment as per the PAANTHER TB treatment decision algorithm

3.2. Secondary study endpoints

1. Time to final TB treatment decision and proportion of children with presumptive TB having completed the PAANTHER TB-treatment decision algorithm

The algorithm will be considered completed if a decision to initiate TB treatment has been taken at any step of the algorithm or if TB has been excluded after systematic evaluation, and all steps planned in the algorithm have been implemented.

 Proportion of cases considered as unlikely TB by the Expert Committee in those initiated on treatment as per the PAANTHER TB treatment decision algorithm (false positive) 3.

- a. Morbidity (drug-induced toxicity ART and TB treatment-related, opportunistic infections, IRIS), with or without TB treatment, and mortality at 6 months
- b. Time to ART initiation in ART-naïve children
- c. CD4 (absolute count and %) gain
- 4. Weight gain at 6 months (absolute value and percentage of body weight), TB symptoms resolution and outcomes in children on TB treatment
- 5. Time to IPT initiation and proportion of children initiated on IPT in those not initiated on treatment as per PAANTHER TB treatment decision algorithm
- Discrimination (area under the receiver-operating-characteristic curves [AUROC]) and calibration measures of the PAANTHER prediction model including or not MLR and CRP, against the TB composite reference standard as defined by the Expert Committee
- 7. Proportion of NPAs (or sputum) and stool samples with *mycobacterium tuberculosis* (MTB) detected using Ultra
- 8. Feasibility defined as proportion of children with NPA and stool samples collected as per study protocol

Safety defined as proportion of NPA with AEs (vomiting, nose bleeding, low oxygen saturation, respiratory distress) occurring during NPA and

Tolerability defined as discomfort/pain/distress experienced by the child during NPA as assessed by the child (Wong-Baker face scale), by the parents (visual analog scale), by the nurses (FLACC behavioral scale) (quantitative assessment) in a subset of children

- Diagnostic accuracy (false negative and false positive rates i.e. NPV and PPV and corresponding sensitivity and positivity) of the PAANTHER algorithm in the different subgroups in terms of age, CD4 counts, nutritional statuses, and timings of ART initiation (on/off ART)
- 10. Incremental cost-effectiveness ratio (ICER)

3.3. Reference diagnosis/case definitions and validation by the Endpoint Review Committee and the international Expert Committee

An Endpoint Review Committee will be set up at the national level for the purpose of case review and validation of TB diagnosis. The national Endpoint Review Committee will review and validate all new TB cases in children initially non-treated for TB, using the updated Clinical Case Definitions for Classification of Intrathoracic Tuberculosis in Children (see Table 2). The Endpoint Review Committee will also validate differential clinical and other diagnoses on opportunistic infections and adverse events. All reviews will be performed following Standard Operating Procedures (SOPs) specifically developed for the study.

Additionally, at the international level, an Expert Committee will be set up for the purpose of clinical validation of TB diagnosis, including identification of children with unlikely TB in those initiated on treatment as per the PAANTHER TB treatment decision algorithm. The International Expert Committee will validate final TB diagnosis and will determine, based on timing, clinical features, and any other relevant information whether missed TB cases are false negatives, potential TB unmasking IRIS or new TB infections. The use of the updated Clinical Case Definitions for Classification of Intrathoracic Tuberculosis in Children will not be possible as treatment decision is not clinician based but algorithm-guided. The Expert Committee will also review part of all cases reviewed at country level to ensure homogeneity of classification across countries (See figure 2).

The Clinical Case Definitions for Classification of Intrathoracic Tuberculosis in Children were initially developed for children with suspected TB and may not be fully relevant for children with HIV infection [59]. They may be revised by the Scientific Advisory Board (SAB) based on current state of the art on time of final case review.

For the purpose of reference diagnosis and case definition, CXRs will be read by 2 independent experts experienced in reviewing CXRs in children, blinded to all of the clinical information and to each other's interpretation. In case of disagreement, advice from a third expert will be sought. For routine care, CXR will be read by the site clinician.

 Table 2. Updated Clinical Case Definitions for Classification of Intrathoracic Tuberculosis in

 Children (adapted from Graham et al, 2015 [59])

| Case definition | Refined criteria | | | |
|-----------------------------|---|--|--|--|
| Confirmed tuberculosis | Bacteriological confirmation obtained (Mycobacterium tuberculosis confirmed by culture or Xpert MTB/RIF assay from at least 1 respiratory specimen) | | | |
| | Bacteriological confirmation NOT obtained AND at least 2 of the following: | | | |
| | Symptoms/signs suggestive of tuberculosis¹ | | | |
| | CXR consistent with tuberculosis ² | | | |
| Unconfirmed tuberculosis | • Close tuberculosis exposure or immunologic evidence of M. tuberculosis infection | | | |
| | Positive response to tuberculosis treatment (requires documented positive clinical response on tuberculosis treatment—no time duration specified) | | | |
| | AND no spontaneous improvement of symptoms in the absence of antituberculosis treatment | | | |
| Unlikely tuberculosis | Bacteriological confirmation NOT obtained AND criteria for "unconfirmed tuberculosis" NOT met | | | |
| | (including spontaneous improvement of symptoms in the absence of antituberculosis treatment) | | | |

¹ Clinical signs/symptoms suggestive of tuberculosis include: (a) Persistent cough: persistent (>2 wk), unremitting cough. (b) Weight loss/failure to thrive: (b1) Unexplained weight loss: >5% reduction in weight compared with the highest weight recorded in last 3 mo OR (b2) Failure to thrive defined as (i) Clear deviation from a previous growth trajectory, and/or (ii) Documented crossing of percentile lines in the preceding 3 mo, and/or (iii) Weight-forage z score of \leq -2 in the absence of information on previous/recent growth trajectory, and/or (iv) Weight-forheight z score of \leq -2 in the absence of information on previous/recent growth trajectory AND (b3) Not responding to nutritional rehabilitation (or antiretroviral therapy if HIV infected). (c) Persistent unexplained fever: Persistent (>1 wk) and unexplained fever (>38°C) reported by a guardian or objectively recorded at least once. (d) Persistent, unexplained lethargy or reduced playfulness: persistent, unexplained lethargy or decrease in playfulness/activity reported by the parent/caregiver. (e) Infants 0–60 d (or neonate): additional signs and symptoms suggestive of tuberculosis include: (e1) neonatal pneumonia or (e2) unexplained hepatosplenomegaly or (e3) sepsis-like illness.

² CXR will be considered consistent with tuberculosis if reviewers agree on the presence and location (right/left) of \geq 1 lesion among the following: alveolar opacity, bronchial compression, excavation, ghon focus, gibbus, miliary, nodular infiltrates, paratracheal nodes, peri-hilar nodes, pleural effusion, tracheal compression (as suggested by Graham et al. 2012 [62]).

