7.3. Patient schedule

| | Protocol visit | | | | | | | |
|---|----------------|-------|---------------------------------------|-------------------------------|-----------------------------|-----------------------------|-----------------------------|-----------------------------|
| | D0 | D1-D2 | D7 ¹ (+/- 1 day) | D15 (+/- 2 days) | Month 1 (+/- 2 weeks) | Month 2 (+/- 2 weeks) | Month 3 (+/- 2 weeks) | Month 6 (+/- 2 weeks) |
| Eligibility criteria | Х | | | | | | | |
| Informed consent(s) | х | | | | | | | |
| Clinical evaluation | х | | Х | Х | Х | Х | Х | Х |
| Medical history | Х | | Х | Х | Х | Х | Х | Х |
| Abdominal Ultrasonography | Х | | | | | | | |
| CXR | Х | | (X) ⁴ | (X) ⁴ | (X) ⁴ | Х | (X) ⁴ | Х |
| TB treatment decision algorithm scoring ² | х | х | | | | | | |
| TB treatment (if required) | Х | Х | Х | Х | Х | Х | Х | Х |
| TB drug adherence assessment | | | Х | Х | Х | Х | Х | Х |
| TB treatment response | | | Х | Х | Х | Х | х | Х |
| LTBI treatment (IPT or RH 3 Mo) ³ | | Х | Х | Х | Х | Х | Х | Х |
| Treatment and care of co- morbidities if needed | х | х | Х | Х | | | | |
| Lab assessment: | | | | | | | | |
| - Complete blood count (CBC) | Х | | | | | Х | | Х |
| - Transaminases and CRP | Х | | | | | Х | | Х |
| - CD4 count | Х | | | | | | | Х |
| NPA | Х | | | | | | | |
| Stool sample | Х | | | | | | | |
| Two GAs or expectorated sputum | | Х | (X) ⁴ | (X) ⁴ | (X) ⁴ | (X) ⁴ | (X) ⁴ | |
| Xpert MTB/RIF Ultra | Х | Х | (X) ⁴ | (X) ⁴ | (X) ⁴ | (X) ⁴ | (X) ⁴ | |
| Mycobacterial culture ⁵ | | Х | (X) ⁴ | (X) ⁴ | (X) ⁴ | (X) ⁴ | (X) ⁴ | |
| NPA safety and tolerability | Х | | | | | | | |
| Biobank (frozen samples): | | | | | | | | |
| - Whole blood | х | | | | | | | |
| - Plasma | Х | | | | | | | |
| - Urine | Х | | | | | | | |
| NPA, sputum and stool leftovers | х | | | | | | | |
| Maximum number of tubes collected ⁶ | 5 | | | | | 2 | | 3 |
| Maximum volume of blood collected ⁷ | 10.5 mL | | | | | 4 mL | | 6 mL |

- (1) Day 7 visit is performed only in children not initiated on TB treatment as per the PAANTHER treatment decision algorithm
- (2) TB treatment decision using the algorithm is taken as soon as the individual score is >100, or once the final score remains <100 and all tests have been performed

- (3) In those not initiated on treatment as per PAANTHER TB treatment decision algorithm
- (4) Performed in children with TB excluded by the algorithm, not improving or deteriorating clinically during followup

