7.6. Treatments

• TB treatment initiation

TB treatment using 2HRZ(E)/4RH with new paediatric formulations according to National Guidelines will be initiated in children with a score≥100. Children with rifampicin resistance detected by Ultra will have culture and phenotypic drug sensibility testing (DST) performed on leftovers from NPAs and stool (and additional samples if needed), and will be started on empirical MDR-TB treatment. Arrangements will be made with NTPs for fast-track MDR-TB treatment initiation.

• Isoniazid Preventive Therapy

As recommended per WHO 2011 "Guidelines for intensified tuberculosis case-finding and isoniazid preventive therapy for people living with HIV in resource-constrained settings", children not initiated on treatment as per PAANTHER TB-treatment decision algorithm will be initiated as soon as possible on IPT or an alternative treatment for latent TB infection (LTBI), such as 3RH [65], as locally available in-country.

• Evaluation of adherence

Adherence to the TB treatment will be evaluated by pill count except in case of Directly Observed Therapy.

• Antiretroviral treatment

ART will be started following national recommendations. As recommended by WHO, this should be done within 2 to 8 weeks of TB treatment initiation in children diagnosed with TB, and not later than 2 weeks in children with CD4 count below 50 cells/µL [66]. In children already on ART, a change of antiretroviral regimen will be considered if appropriate (e.g. switch from nevirapine or lopinavir to efavirenz, or double boosting of lopinavir if possible in accordance with National Guidelines).

• Associated treatments

Prophylactic treatments for opportunistic infections (Cotrimoxazole +/- Fluconazole) may be prescribed according to the recommendations of national programs, as well as Isoniazid prophylaxis in case TB diagnosis is ruled out by the clinician.

• Treatment dispensing

Anti-tuberculosis and antiretroviral drugs will be provided by national authorities. They will be dispensed in accordance with each hospital's procedures. Their access will be free of charge for patients in accordance with the recommendations of national protocols.

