Primary endpoint:

Proportion of missed TB cases (false negative cases) in children not initiated on treatment as per the PAANTHER TB treatment decision algorithm

Secondary endpoints:

1.Time to final TB-treatment decision and proportion of children with presumptive TB having completed the PAANTHER TB treatment decision algorithm.

The algorithm will be considered completed if a decision to initiate TB treatment has been taken at any step of the algorithm or if TB has been excluded after systematic evaluation, and all steps planned in the algorithm have been implemented.

2. Proportion of cases considered as unlikely TB by the Expert Committee in those initiated on treatment as per the PAANTHER TB treatment decision algorithm (false positive)

3. a. Morbidity (drug-induced toxicity – ART and TB treatment-related, opportunistic infections, IRIS) with or without TB treatment, and mortality at 6 months;

b. Time to ART initiation in ART-naïve children;

c. CD4 (absolute count and %) gain.

4. Weight gain at 6 months (absolute value and percentage of body weight), TB symptoms resolution and outcomes in children on TB treatment

5. Time to IPT initiation and proportion of children initiated on IPT in those not initiated on treatment as per PAANTHER TB treatment decision algorithm

6. Discrimination (area under the receiver-operating-characteristic curves [AUROC]) and calibration measures of the PAANTHER prediction model including or not MLR and CRP, against the TB composite reference standard as defined by the Expert Committee

7. Proportion of NPAs (or sputum) and stool samples with positive TB detection using Ultra

8. Feasibility defined as proportion of children with NPA and stool samples collected as per study protocol;

Safety defined as proportion of NPA with AEs (vomiting, nose bleeding, low oxygen saturation, respiratory distress) occurring during NPA, and

Tolerability defined as discomfort/pain/distress experienced by the child during NPA as assessed by the child (Wong-Baker face scale), by the parents (visual analog scale), by the nurses (FLACC behavioural scale) (quantitative assessment) in a subset of children

9. Diagnostic accuracy (false negative and false positive rates i.e. NPV and PPV and corresponding sensitivity and positivity) of the PAANTHER algorithm in the different subgroups in terms of age, CD4 counts, nutritional statuses, and timings of ART initiation (on/off ART)

10. Incremental cost-effectiveness ratio (ICER)

Study design:

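### Secondary endpoint 3a counts toxicity of ART and TB treatment only, so as worded it leaves out toxicity of the preventive TB drugs given to the untreated group

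*Protocol*

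**What the plan says.** Objective 3a (section 2.2) is to assess "Incidence of morbidity (drug toxicity, opportunistic infections, IRIS) and mortality during 6 months after enrolment". The lead-in to objective 3 sets the contrast: "including comparison of those initiated and those not initiated on TB treatment as per the PAANTHER TB treatment decision algorithm, to assess". The objective does not limit which drugs' toxicity is meant.

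Endpoint 3a (section 3.2) reads "Morbidity (drug-induced toxicity ART and TB treatment-related, opportunistic infections, IRIS), with or without TB treatment, and mortality at 6 months". The protocol summary in Appendix 1 carries the same restriction: "ART and TB treatment-related, opportunistic infections, IRIS) with or without TB treatment, and mortality at 6 months".

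Section 7.6 describes two separate regimens. For the treated group, "TB treatment using 2HRZ(E)/4RH with new paediatric formulations according to National Guidelines will be initiated". Under its own heading, "children not initiated on treatment as per PAANTHER TB-treatment decision algorithm will be initiated as soon as possible on IPT" or an alternative latent-TB regimen such as 3RH. The visit schedule in section 7.3 gives the preventive regimen its own row, beginning "LTBI treatment (IPT or RH 3 Mo", apart from the TB treatment row.

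Section 9.3 has every adverse event entered in the CRF. Its list of examples again names only ART and TB treatment as sources of drug toxicity.

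**The concern.** The endpoint is narrower than the objective it serves, and the gap falls on one side of a planned comparison. Children who start TB treatment receive isoniazid and rifampicin as part of that treatment, and toxicity from them counts. Children who do not start it are meant to receive isoniazid, or rifampicin with isoniazid, as prevention. Toxicity from those same drugs is not among the classes the endpoint names.

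Read this way, the endpoint would understate drug toxicity in the untreated group and make withholding treatment look slightly safer than it is. That bears on the benefit-risk picture, because the Introduction lists cumulative drug toxicity as a cost of treating children who turn out unlikely to have TB. No other endpoint closes the gap: endpoint 5 covers only the timing and uptake of preventive therapy.

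**Working it through.** **Does TB treatment, as the protocol uses the term, include preventive therapy?**

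- Endpoint 3a uses the term twice in one sentence. The children without TB treatment are the ones section 7.6 plans for preventive therapy. If preventive therapy were TB treatment, the with-or-without phrase would lose its meaning.
- The primary endpoint (section 3.1) and endpoint 5 (section 3.2) are both defined in children not initiated on treatment. Endpoint 5 then measures the start of preventive therapy in those same children, so preventive therapy must fall outside treatment.
- Section 7.6 defines TB treatment as 2HRZ(E)/4RH and handles preventive therapy under a separate heading. Section 7.3 gives it a separate row.
- Section 5.1.2 exempts preventive isoniazid or rifampin/isoniazid from exclusion. That exemption qualifies anti-TB drugs, not TB treatment, so it does not settle the question either way.

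The most natural reading therefore excludes preventive drugs from the toxicity component. Section 7.6 also allows other drugs outside the endpoint's wording ("Prophylactic treatments for opportunistic infections (Cotrimoxazole +/- Fluconazole) may be prescribed according to the recommendations of national programs"), but these are not tied to one group and do not create the same imbalance.

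**How many children are affected?** Section 4.3 assumes prevalence 50%, sensitivity 89%, specificity 61% and 550 children.

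- Algorithm-negative share = 0.50 × (1 − 0.89) + 0.50 × 0.61 = 0.055 + 0.305 = 0.36.
- Check against the plan's own figure: missed cases among the algorithm-negative = 0.055 / 0.36 = 15.3%, which agrees with the 15% in section 4.3.
- Expected algorithm-negative children = 550 × 0.36 = 198. This is an expected count. Children scoring below 100 who are treated because of a severe condition would lower it.
- Expected missed cases = 198 × 0.15 = 29.7. These children would start TB treatment later, and toxicity on that treatment counts even on the narrow reading.
- Remaining = 198 − 29.7 = 168.3.

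**How many events could be left out?** The protocol gives neither uptake nor a toxicity rate for preventive therapy. I assume uptake of 50-100% and toxicity of 1-5%. Omitted events = 168.3 × uptake × toxicity.

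| Uptake | Toxicity | Omitted events |
|---|---|---|
| 50% | 1% | 0.84 |
| 100% | 1% | 1.7 |
| 50% | 5% | 4.2 |
| 100% | 5% | 8.4 |

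As a share of the 198: 0.84 / 198 = 0.4 and 8.4 / 198 = about 4.3 percentage points. If the later-treated children also took preventive drugs first and had toxicity at the top rate, the figure would be 198 × 1.0 × 0.05 = 9.9 events.

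**The case against.** The strongest reply is that this is a matter of drafting. Section 9.3 ties the documentation of morbidity to all adverse events, and its list is illustrative. Section 7.7 applies the same laboratory tests, transaminases included, to every child. The IDMC receives overall morbidity data for the untreated group (sections 11.2.2 and 13.3). The endpoint can also be read alongside its unrestricted objective, with ART and TB treatment as shorthand for the main drug families. Section 11.2.3 leaves further detail on secondary endpoints to the SAP, which is not at hand.

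On size, the uptake and toxicity rates are assumed, and the upper figures sit at the top of the assumed ranges. Some events in children on ART would be attributed to ART and so still count. The Introduction says the start of preventive therapy may depend on immune suppression, so full uptake is a ceiling.

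Much of this stands. No data are lost, the looser reading is possible, and the low end of the range is more credible: section 9.2 describes anti-TB drugs as very well tolerated in children. It does not remove the point, though. Recording an event is not the same as counting it in an endpoint, and an IDMC report is not the endpoint. What is left to the SAP is the analysis of secondary endpoints, whereas their scope is set in section 3.2. The looser reading also runs against the protocol's own use of the term.

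**Conclusion.** The point holds and is minor. As worded, endpoint 3a is narrower than objective 3a and omits preventive-drug toxicity in the untreated group only. Confidence is medium, because the parenthesis can be read more loosely.

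On the assumed rates, the omission amounts to about 0.8 to 8.4 events, or 0.4 to 4.3 percentage points of the untreated group's toxicity rate. The documents cannot fix the figure within that range.

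Only the drug-toxicity part of one non-randomised secondary comparison is touched. The NPV on which validation rests, mortality, opportunistic infections, IRIS and ART toxicity are unaffected.

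**What to change.** In section 3.2 and in Appendix 1, reword the toxicity component of endpoint 3a to: drug-induced toxicity (ART, TB treatment and LTBI treatment-related). That change is sufficient. Two optional additions would help: name LTBI treatment among the examples in section 9.3, and report toxicity by drug class in both groups.

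The cost is a few words. Adverse events, treatments and transaminases are already collected in both groups (sections 7.7, 9.3 and 10.1.1). The remaining burden is attributing events to a drug class in children who are also on ART. The untreated group's toxicity figure may come out slightly less favourable.

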5. STUDY ENROLLMENT

5.1. Study population

5.1.1. Inclusion criteria

- 1. Children aged 1 month to 14 years
- 2. Documented HIV-infection (i.e., confirmed before entry into the study)
- 3. Presumptive TB based on at least one criteria among the following¹:
 - a. Persistent cough for more than 2 weeks
 - b. Persistent fever for more than 2 weeks
 - c. Recent failure to thrive (documented clear deviation from a previous growth trajectory in the last 3 months or Z score weight/age < 2)
 - d. Failure of broad spectrum antibiotics for treatment of pneumonia
 - e. Suggestive CXR features

OR

History of contact with a TB case and any of the symptoms listed under point 3 with a shorter duration (< 2 weeks)

¹ PAANTHER inclusion criteria

4. Informed consent signed by parent/guardian

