7.7. Follow-up

All children will be followed-up for 6 months upon enrolment, with systematic study visits at day 15, month 1, 2, 3, and 6. In children not initiated on TB treatment as per the PAANTHER treatment decision algorithm, an extra visit will be performed at day 7 for an early detection of missed TB cases. The dates of each visit must comply with the provisional patient schedule generated from the date of inclusion of the child. For month 1 to month 6 visits, a flexibility of +/- 2 weeks around theoretical dates of protocol visits will be allowed to enable study visit to coincide with routine ART and HIV follow-up visits. If a child fails to attend a study follow-up visit, the clinical team on site will confidentially contact the parent(s)/guardian(s) and encourage/assist them to bring back the children for follow-up.

Each visit will comprise:

- Clinical evaluation: complete physical examination, vital signs, nutritional status
- Medical history since the last visit: any new clinical and AE with special attention to drug tolerance and TB paradoxical reaction
- CXR to detect new or aggravated lesions (at M2 and M6 final visit)
- Laboratory assessment: CBC, transaminases and CRP at M2 and M6 visit, CD4 count at M6 visit
- Evaluation of adherence to TB treatment, if initiated
- Any change of ART occurring during the study follow-up
- Study drug prescription and dispensation to cover time to the next follow-up visit

In case of TB treatment failure or unfavourable evolution, appropriate samples will be performed and resistance to TB drugs will be assessed using methods available on sites (phenotypic DST or line probe assays).

In children not initially diagnosed with TB, who show no clinical improvement or present additional signs of presumptive TB at day 7, 15, M1, M2, or M3, bacteriological specimen collection and Ultra testing will be repeated. These will include standard samples, i.e. GA or expectorated sputum. CXR could also be repeated, in addition to M2 and M6 visits, for children with clinical signs suggestive of TB at other scheduled or unscheduled study visit.

During the last follow-up visit at month 6, an assessment of the TB disease evolution and response to treatment will be made (cured, treatment failure, continuation of TB treatment, death, lost to follow-up).

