10. DATA COLLECTION AND PROCESSING

10.1. Description of data collected

10.1.1. Individual patient data

Once enrolled in the study, the following data will be collected for each patient by study nurses and/or site investigators, on remote data capture devices:

- Individual identifiers: month and year of birth, sex
- Anthropometric and clinical data: weight, height, vital signs, symptoms, treatments and adherence, AEs
- Data on the tolerability of NPA collection (qualitative and quantitative)
- Radiological and ultrasonography data: digital images and interpretation
- Laboratory data: mycobacterial culture and Ultra assay, blood tests
- Samples collected for biobanking
- TB treatment, if initiated
- Comorbidity management: antiretroviral treatment, treatment of other opportunistic infections, other
- Outcome data: end of study status or early study termination (death, lost to follow-up, withdrawal)

For each new patient included in the study, an anonymised individual identification code will be attributed and used as the only patient identifier in the REDCap database.

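### The weight component of secondary endpoint 4 is unstandardised gain over 6 months in children from 1 month to 14 years of age, so it confounds recovery with age and normal growth

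*Protocol*

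**What the plan says.** Section 3.2 of the protocol gives secondary endpoint 4 as "Weight gain at 6 months (absolute value and percentage of body weight), TB symptoms resolution and outcomes in children on TB treatment", and Appendix 1 repeats it in the same words. It serves objective 4 in section 2.2: "To assess TB treatment outcomes in HIV-infected children initiated on treatment as per the PAANTHER TB treatment decision algorithm". The population is "Children aged 1 month to 14 years" (section 5.1.1), and section 7.7 sets the period: "All children will be followed-up for 6 months upon enrolment".

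For this endpoint the protocol names no Z-score change, growth reference, age stratification or untreated comparator. Section 11.2.3 leaves further detail on the analysis of secondary endpoints to the statistical analysis plan, which is not among the documents.

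The means of standardising are present. Section 10.1.1 lists "Anthropometric and clinical data: weight, height, vital signs, symptoms, treatments and adherence, AEs" and "Individual identifiers: month and year of birth, sex". Each follow-up visit includes "Clinical evaluation: complete physical examination, vital signs, nutritional status" (section 7.7), and section 7.4 counts weight and height among the vital signs. Weight-for-age Z scores are already used in the failure-to-thrive entry criterion (section 5.1.1) and, with weight-for-height Z scores, in the footnotes to Table 2 (section 3.3).

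**The concern.** Over 6 months a growing child gains weight with or without recovery, and by an amount that depends heavily on age. A raw gain, in absolute terms or as a percentage, therefore mixes two things: growth that would have happened anyway, and catch-up after illness. Only the second bears on objective 4.

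Two readings become unsafe. A positive average gain in treated children may be taken as a sign of response when some or all of it is ordinary growth. And if gains are averaged over all ages, or set beside those of another group, a difference may reflect the age mix instead of recovery. The endpoint is defined only in children on treatment, so no comparison group shows how much growth to subtract.

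**Working it through.** The plan states no figure for this endpoint, so there is nothing to reproduce. The check is whether either scale removes the dependence on age.

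**Step 1. Does a percentage remove it?** Percentage gain = 100 × gain / starting weight. For the same 2 kg gain:
- starting weight 5 kg: 100 × 2/5 = 40%
- starting weight 20 kg: 100 × 2/20 = 10%
- starting weight 40 kg: 100 × 2/40 = 5%

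The same absolute gain differs eightfold as a percentage across these starting weights, so the two scales cannot both be comparable across ages. Step 2 suggests that neither is.

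**Step 2. What gain corresponds to no recovery?** The documents give no growth figures. The values below are assumptions for 6 months of growth without catch-up, shown as ranges.

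| Group (assumed) | Low case | High case | Percentage gain |
|---|---|---|---|
| Infant | 4 kg, +2.0 kg | 5 kg, +3.5 kg | 50.0 to 70.0 |
| Toddler | 10 kg, +0.8 kg | 12 kg, +1.4 kg | 8.0 to 11.7 |
| School age | 20 kg, +1.0 kg | 30 kg, +2.0 kg | 5.0 to 6.7 |
| Adolescent | 35 kg, +1.5 kg | 45 kg, +3.0 kg | 4.3 to 6.7 |

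Every group gains with no recovery at all, and the size of the gain follows age.

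**Step 3. How far could age mix move an average?** With a share s of young infants, mean gain = s × (infant gain) + (1 − s) × (older-child gain). Moving s by 10 percentage points changes the mean by 0.10 × (infant gain − older-child gain). With the school-age and adolescent values above as the older group:
- smallest contrast: 0.10 × (50 − 6.7) = 4.3 percentage points
- largest contrast: 0.10 × (70 − 4.3) = 6.6 percentage points

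This shows direction only. Section 1 reports a median age of 7.3 years (IQR 3.3 to 9.7) in the development study. About a quarter of those children were under 3.3 years, a group that includes toddlers as well as infants, so a large share of 5 kg infants is unlikely.

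**Step 4. Who is in the treated group?** Section 4.3 assumes sensitivity 89%, specificity 61% and prevalence about 50%. Algorithm-positive children with TB: 0.5 × 0.89 = 0.445. Without TB: 0.5 × (1 − 0.61) = 0.195. Share without TB: 0.195 / (0.445 + 0.195) = 0.195/0.640 = 30%. Their ordinary growth would also be counted as weight gain on TB treatment.

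**Step 5. Is a better measure within reach?** Weight, height, sex, and month and year of birth are recorded, so a standardised score can be computed at D0 and M6. The protocol accepts Z scores for judging poor weight at entry and in Table 2, but does not use them to judge recovery.

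**The case against.** The strongest reply is that weight is only one part of the endpoint. The same sentence names symptom resolution and outcomes, section 7.7 adds a month 6 assessment of disease evolution and response, and the schedule in section 7.3 lists treatment response at successive visits. This stands. A reader might infer that endpoint 4 as a whole cannot show treatment response; the documents do not support that.

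Second, weight gain is not empty of information. It includes catch-up growth, and the protocol treats weight loss and departure from a growth trajectory as signs of TB. For a child enrolled while falling off a trajectory, holding a constant centile may itself be improvement. This also stands: the measure is confounded, not uninformative.

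Third, no comparison of weight gain between countries or subgroups is planned. The country-wise and age analyses in section 11.2.3 concern the score's performance. A reader might infer that country comparisons will be distorted, but that would follow only if someone made them.

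Fourth, the analysis plan may add age strata or Z scores. It may, but section 11.2.3 defers only analysis detail. The variable itself is fixed in section 3.2 and again in Appendix 1.

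Fifth, Table 2 also uses an unstandardised percentage, a weight loss above 5%, at all ages. That is a loss, which normal growth works against. A gain is what normal growth produces, so the parallel is weak.

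**Conclusion.** The point holds for the weight component alone. As defined, it confounds recovery with age and normal growth, and expressing the gain as a percentage does not cure this. The Step 1 arithmetic needs no growth assumption. The sizes in Steps 2 and 3 rest on assumed growth and an assumed age mix, and should be read as illustration, not forecast.

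The reach is limited to one component of one secondary endpoint. The primary endpoint, the sample size and the rule for validating the algorithm are untouched. The change is still worth making, because the better measure is already used elsewhere in the protocol and the data for it are already collected.

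**What to change.** In section 3.2 and Appendix 1:
- Define the weight component of endpoint 4 as the D0 to M6 change in an age- and sex-standardised score: weight-for-age Z score, or BMI-for-age Z score at ages where the chosen reference has no weight-for-age values.
- Name the growth reference.
- Leave symptom resolution and outcomes as they are. Replacing the whole endpoint with a Z-score change would drop the parts that serve objective 4 most directly.
- Report absolute and percentage gain descriptively by age group.

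The cost is a change of wording. No visit or measurement is added, provided that height is taken at M6 as section 7.4's list of vital signs implies. There are two drawbacks. Only month and year of birth are recorded, so Z scores will be slightly less precise in the youngest infants. And a Z-score change does not separate the effect of TB treatment from that of ART or nutritional recovery, so it should not be presented as a treatment effect.
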